### 8.3 Measures

Participants will be asked to complete questionnaires at baseline, mid-treatment (after 6 sessions), posttreatment (after 12 sessions), at a 3-month follow-up, and at a 6-month follow-up. Baseline, mid-treatment, and posttreatment assessments will be completed on tablets with a link from REDcap, though participants will have the option to

respond on paper forms. Both follow-up assessments will be carried out online with a link sent via email. The primary outcome tool for this study will be the six-item Urinary Distress Inventory (UDI-6), which is a subscale of the Pelvic Floor Distress Inventory (PFDI), as measure of urinary symptoms. We will also measure anxiety using a short form from the NIH Patient Reported Outcomes Measurement Information System (PROMIS), which has been shown to be reliable and valid; this form is brief and easy to complete. Secondary measures include the PROMIS profile (depression, fatigue, pain, physical function, sleep disturbance, and social roles), trauma history assessed with the PTSD Checklist for DSM-5 with Life Events Checklist (PCL-5), the Mini-IPIP, a 20-item short form of the International Personality Item Pool measure of the Big Five personality traits, the Ruminative Responses Scale (RRS) short form, and the Patient Global Impression of Improvement (PGI-I) – a one item self-report assessment of improvement of urinary symptoms. In addition, at both follow-up assessments, participants will be asked whether they have received any treatment outside of the study for their urinary symptoms and/or their anxiety. Any treatment participants receive outside of the study will be tracked in this manner and included in data analyses.

Table 2. Timing of Assessments

Measure	Estimated Completion Time	Baseline	Session 6	Session 12	3 Month Post-Treatment Follow-up	6 Month Post-Treatment Follow-up
Medical history and physical exam	0 (part of regular medical visit and extracted from EMR)	X				
Demographic questionnaire	1 min	X				
Single Item Literacy Screener (SILS)	< 1 min	X				
Brief Medication Questionnaire (BMQ) 	3-5 min	X			X	X
Primary outcome 1: PROMIS Anxiety subscale of profile (4 of 29 items below)	See below for entire profile	X	X	X	X	X
Primary outcome 2: Urinary symptoms using the Urinary Distress Inventory (UDI-6) of the Pelvic Floor Distress Inventory (PFDI)	1-3 min	X	X	X	X	X

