### 8.5 Analysis Plan

**Primary analyses.** We will create hierarchical linear models (HLM) to test the primary hypotheses of the study. One model will determine the effect of type of therapy on anxiety. A separate model will determine the effect of type of therapy on urinary symptoms. The dependent variables for these models will be the UDI-6 subscale of the PFDI-20 and anxiety as measured by the anxiety subscale of the PROMIS Profile-29. The structure of the HLM model is shown below. Note that these models create a response profile for each person across all time points as described in the protocol.

#### Level 1

$$Y = P_0 + P_1(T_2) + P_2(T_3) + P_3(T_4) + P_4(T_5) + E$$

#### Level 2

$$P_0 = B_{00} + B_{01}(\text{Condition})$$

$$P_1 = B_{10} + B_{11}(\text{Condition}) + R_1$$

$$P_2 = B_{20} + B_{21}(\text{Condition}) + R_2$$

$$P_3 = B_{30} + B_{31}(\text{Condition}) + R_3$$

$$P_4 = B_{40} + B_{41}(\text{Condition}) + R_4$$

The dummy variables P1-P4 are dummy codes for the five time points. These will allow us to determine the degree of change from baseline. Each of the "P" coefficients is influenced by Level-2 variables. T2 - T5 are dummy variables of the time differences from baseline. E, R1-R4 represent error terms in the model. Condition will be dummy coded (UP-CBT = 1, Supportive Therapy = 0).

**Testing Key endpoints.** We have two primary endpoints and therefore we will have two models. For both anxiety (PROMIS T score) and urinary symptoms (UDI-6), the full model (see above) will be compared to a reduced model with all of the terms involving condition removed (i.e., B01, B11, B21, B31, and B41). If this comparison is significant ( $p < .05$ ), then we will test individual parameters at a Type I error rate of alpha = .05 (two-tailed). Note, these tests will only be carried out if the full-reduced model comparison is

significant. The key prediction for anxiety is that parameters B21, B31, and B41 (representing the effect of UP-CBT at post-treatment and beyond) will be significant and negative (representing fewer symptoms). The key prediction for urinary symptoms is that parameters B21, B31, and B41 (representing the effect of UP-CBT at post-treatment and beyond) will be significant and negative (representing fewer symptoms).

**Missing data.** All participants with baseline data will be included in the modeling using an intent-to-treat approach. The HLM approach described above can accommodate cases with missing follow-up data.

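### The overall test in 8.5 includes B01, a chance baseline difference, which spends one degree of freedom without adding treatment signal

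*Combined protocol and SAP*

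**What the plan says.** Section 8.5 (Testing Key endpoints) sets one overall test per primary endpoint: the full model "will be compared to a reduced model with all of the terms involving condition removed (i.e., B01, B11, B21, B31, and B41". Individual parameters are reached only through it: "these tests will only be carried out if the full-reduced model comparison is" significant at .05, and each parameter is then tested two-sided at .05.

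The stated prediction is narrower. For both endpoints it is that "parameters B21, B31, and B41 (representing the effect of UP-CBT at post-treatment and beyond) will be significant and negative".

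The coding fixes the meaning of each term. Section 8.5 says that "T2 - T5 are dummy variables of the time differences from baseline", and section 8.3 places the assessments at "baseline, mid-treatment (after 6 sessions), posttreatment (after 12 sessions), at a 3-month follow-up, and at a 6-month follow-up". So B01 is the arm difference at baseline, B11 the arm difference in change to session 6, and B21, B31 and B41 the differences in change to session 12, 3 months and 6 months.

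The Level 2 equation for P0 contains Condition but no error term. No other section narrows the overall test or gives its power.

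**The concern.** Allocation is randomised (section 8.1), so the expected baseline difference is zero. Including B01 has two effects.

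- It adds a numerator degree of freedom with no expected signal, so the overall test is less sensitive to a real effect. If it is not significant, none of the key contrasts is tested.
- A chance imbalance counts towards significance. With B01 free and complete data, the same imbalance also moves the change contrasts the other way. If the UP-CBT arm starts b SD higher by chance and the correlation is ρ, the expected shift in B21 is −(1 − ρ)b, or −0.4b at ρ = .6.

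At stake is some power for the overall test on each primary endpoint, and the clarity of what a significant result means.

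**Working it through.** **The plan's own figure.** Section 4.0 uses d = 1.5, 16 analysed per group and two-sided .05. The noncentrality is 1.5 × √(16/2) = 4.243 on 30 df, which gives power of 98.4% (stated: above 98%). 32/0.80 = 40 randomised. Both reproduce, but they describe a single two-group contrast, not the 5-df test.

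**Assumptions (not in the documents).** 16 per arm, complete data, SD 1, correlation ρ = .6 between every pair of visits, unstructured covariance in the analysis, exact F test. The effect at each visit is d times a weight w, in the order baseline, session 6, session 12, 3 months, 6 months:

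- sustained: 0, .5, 1, 1, 1
- fading: 0, .5, 1, .6, .4
- early then fading: 0, 1, 1, .6, .4

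**Formula.** λ = (16/2) × d² × [1/(1 − ρ)] × [Σw² − (ρ/(1 + 4ρ)) × (Σw)²]. At ρ = .6 this is 20d² × [Σw² − 0.1765(Σw)²].

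- Sustained, d = 0.75: 11.25 × (3.25 − 0.1765 × 12.25) = 11.25 × 1.088 = 12.24
- Fading, d = 0.75: 11.25 × (1.77 − 0.1765 × 6.25) = 11.25 × 0.667 = 7.50
- Fading, d = 1.0: 20 × 0.667 = 13.34
- Early then fading, d = 0.75: 11.25 × (2.52 − 0.1765 × 9) = 11.25 × 0.932 = 10.48
- Sustained, d = 1.5: 45 × 1.088 = 48.97

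**Tests compared.**

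- As written: F on 5 and 26 df, critical value 2.587, noncentrality λ.
- B01 = 0 in both models: F on 4 and 26 df, critical value 2.743, noncentrality λ/(1 + t²/30), averaged over the chance distribution of the baseline t statistic. Because w = 0 at baseline, λ itself is unchanged. Only the df and this small correction differ.
- B01 = 0 and B11 kept in both models: F on 3 and 27 df. Session 6 drops out, so the factor becomes ρ/(1 + 3ρ) = .2143. For sustained d = 0.75, λ = 11.25 × (3 − .2143 × 9) = 12.05; for both fading shapes, 11.25 × (1.52 − .2143 × 4) = 7.46.

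| True effect | 5 df, as written | 4 df, B01 = 0 | 3 df |
|---|---|---|---|
| d = 0.75 sustained | 67.5% | 71.0% | 76.4% |
| d = 0.75 fading | 44.1% | 47.6% | 53.6% |
| d = 1.0 fading | 71.9% | 75.2% | 80.7% |
| d = 0.75 early then fading | 59.7% | 63.3% | 53.6% |
| d = 1.5 sustained | about 100% | about 100% | about 100% |

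Removing B01 gains 3.5, 3.5, 3.3 and 3.6 points in the first four rows. Simulation of the same four rows gave 68.0% to 71.2%, 46.2% to 49.5%, 71.5% to 74.4% and 60.6% to 63.6%, gains of about 3 points each.

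**A repair that backfires.** Leaving B01 free in both models and testing the four raw change contrasts replaces the factor .1765 by 1/5. For sustained d = 0.75, λ = 11.25 × (3.25 − 12.25/5) = 9.0 on 4 and 27 df. Power is 57.8% (59% in simulation), against about 68% as written.

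**No effect at all.** In simulation the exact F test was significant in 5.0% of trials. B01 was individually significant in 1.2% of all trials, about a quarter of those.

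**The case against.** The strongest defence is that nothing is lost at the effect the plan assumes, and that with an exact F test the Type I error is 5% when there is no effect at any visit. Both stand. The baseline-driven results are part of that 5%, not an addition to it. It is also fair that the plan names no test statistic. A likelihood ratio test against chi-square is significant more often, but also in about 9% of trials with no effect at n = 32. Neither point gives B01 a reason to be in the tested set.

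A reader might infer three stronger things that the documents do not support.

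- *That the overall test often blocks a significant post-treatment contrast.* At d = 1.5 sustained this happens in 0.1% of cases or fewer, and in about 2% if the effect fades. It becomes common only well below the planning value: 12%, 25% and 19% of trials in the first three rows of the table. Most of that comes from requiring any multi-df test first. With the 3-df version, the chance that the overall test and B21 are both significant rises from 51% to 56%, 38% to 46% and 69% to 77%, so about 7%, 17% and 11% of trials remain blocked.
- *That the plan expects nothing at session 6.* The mediation analysis in 8.5 posits a path from condition through mid-treatment anxiety to later urinary symptoms, in a stated direction. B11 is outside the key prediction but is not a nuisance term like B01.
- *That dropping B11 as well is plainly better.* The fourth row of the table shows the reverse.

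**Conclusion.** The point holds for B01. It is a chance quantity in a randomised trial, and testing it costs about 3 to 4 points of power for the overall test when the true effect is about 0.75 to 1.0 SD, and essentially nothing at d = 1.5 sustained. The size rests on the assumed correlation of .6, complete data, 16 per arm, an exact F test, an unstructured covariance and the effect shapes listed. Missing data were not modelled, and the gain was not calculated for the covariance structure as printed.

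Whether B11 belongs in the overall test is a choice, not an error. As written, an effect of d = 1.0 confined to session 6 makes the test significant in 57% to 92% of trials (exact F, correlation .3 to .7). A 3-df test on B21, B31 and B41 returns that to 5% and matches the key prediction. It gains power if the effect builds after session 6 and loses power if the effect is full by session 6 and then fades.

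**What to change.** In 8.5, for each endpoint:

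1. Write the P0 equation without Condition (B01 = 0) in both the full and the reduced model, and keep baseline scores in the outcome vector.
2. Specify an unstructured within-person covariance. As printed, P0 has no error term. If E is independent across visits, the model then treats baseline as uncorrelated with later scores, and the constraint could not adjust for baseline.
3. Let the reduced model remove B11, B21, B31 and B41 (4 df).
4. Do not instead leave B01 free in both models and test raw change, which lowers power.
5. Optionally, keep B11 in both models and remove only B21, B31 and B41 (3 df), with the trade-off stated and the choice made before data are seen.

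The cost is a rewritten P0 equation and a statement that baseline questionnaires are completed before allocation is known, which the documents do not currently say. No extra participants or assessments are needed.

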#### **4.0 Sample Size:**

This study will include up to 40 participants. UP-CBT has been shown to have quite large effects (Cohen's  $d$  values of 1.7 or greater). For this study, we have chosen a slightly more conservative estimate for Cohen's  $d$  of 1.5, which represents 1.5 standard deviations between the treatment effect of UP-CBT versus the control group. Based on a power analysis, we would require 16 women per group, in the data analyzed, to detect a treatment effect with  $> 98\%$  power with a Type I error rate of  $\alpha = .05$ , two-tailed. Study withdrawal is estimated at roughly 20%, leaving an estimated final sample of 32 participants for data analysis (see CONSORT diagram below).

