## 8.2 Use of Electronic Medical Record

The electronic medical record (Epic) will be used to extract the following social and medical history. Demographic data (e.g., age, date of birth, gender, race/ethnicity, and insurance type) will be obtained from the patient’s electronic medical record, and verified via self-report. Demographic variables will likely be used as covariates in analyses. Results of physical examinations, particularly urological and gynecological history as well as urinary symptoms, will be used to determine inclusion criteria. History and diagnoses of serious illness that would preclude study participation will be extracted to determine exclusion criteria (see section 3.2 above). In addition, substance and alcohol use history and diagnoses will be accessed through Epic to establish the exclusion criterion of substance use disorder. Lastly, mental health history and diagnoses will be pulled from Epic for inclusion/exclusion criteria, and to provide background information for therapists.

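### The primary model leaves the baseline arm difference free, counts it in the five-term gate, and does not use the baseline score to reduce variance

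*Combined protocol and SAP*

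**What the plan says.** Section 8.5 models each primary outcome (PROMIS anxiety and UDI-6) over five visits, with dummy variables T2 to T5 for change from baseline. The Level 2 equation for the intercept contains Condition, so B01, the difference between arms at baseline, is estimated freely. Condition is the only Level 2 predictor in any equation.

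The gate compares this full model with a "reduced model with all of the terms involving condition removed (i.e., B01, B11, B21, B31, and B41"). Single parameters are tested at two-sided 0.05 only if the gate is significant. The key predictions concern B21, B31 and B41.

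On the random part, the plan says "E, R1-R4 represent error terms in the model". The intercept P0 has no random term. On missing data, "All participants with baseline data will be included in the modeling using an intent-to-treat approach".

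The only statement on covariates is in 8.2: "Demographic variables will likely be used as covariates in analyses". It does not mention the baseline outcome score.

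Section 4.0 plans on "1.5 standard deviations between the treatment effect of UP-CBT versus the control group" and says "we would require 16 women per group, in the data analyzed, to detect a treatment effect". It does not say whether the SD is that of a single score or of a change score.

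**The concern.** Randomisation makes the true pre-treatment difference zero. Estimating it freely has two consequences. The gate spends one of its five degrees of freedom on a term that cannot show a therapy effect. And each key contrast becomes a difference in raw change, which carries the full noise of the baseline score. Adjusting for that score never has larger variance in large samples, and the score is already collected.

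This is a loss of efficiency, not of validity: a free B01 does not inflate the type I error. It matters because only about 32 women are expected in the analysis and d = 1.5 is a very large planning effect. If the true effect is smaller, power is given up that would cost nothing to keep.

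**Working it through.** **The plan's own figure.** With 16 per arm, d = 1.5 and two-sided 0.05, the noncentrality is 1.5 × √(16/2) = 4.24 on 30 df. Power is 98.4%, in line with the stated figure of more than 98%. And 40 × 0.8 = 32.

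**Assumptions.** The documents give neither the baseline to follow-up correlation (rho) nor any SD. I take rho = 0.2, 0.5 and 0.9, and k = follow-up SD / baseline SD = 0.8, 1 and 1.25, with complete data and 16 per arm. All efficiency and power figures assume a correctly modelled covariance, which the printed model does not have (see below).

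**Variance.** In units of the baseline variance, and leaving out the common factor 2/n:
- raw change: 1 + k² − 2·rho·k
- adjusted for baseline: k²(1 − rho²), times 1 + 1/28 with 32 women

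With k = 1 these are 2(1 − rho) and 1 − rho², so the large-sample saving is (1 − rho)/2. At rho = 0.5: raw 1.00, adjusted 0.75, saving 25%. With 32 women: 0.75 × 29/28 = 0.777, saving 22%.

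Variance saved, large sample / 32 women:

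| k | rho 0.2 | rho 0.5 | rho 0.9 |
|---|---|---|---|
| 0.8 | 53.5 / 51.8% | 42.9 / 40.8% | 39.2 / 37.0% |
| 1 | 40 / 38% | 25 / 22% | 5 / 2% |
| 1.25 | 27.3 / 24.7% | 10.7 / 7.5% | 5.0 / 1.6% |

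The worst case is rho × k = 1, for example 0.8 × 1.25. Raw change is then 1 + 1.5625 − 2 = 0.5625 and adjusted is 1.5625 × 0.36 = 0.5625. There is no saving in large samples, and the variance is 3.6% larger (29/28) with 32 women.

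**Power of the B21 test.** Noncentral t, k = 1, 30 df for raw change and 29 df for adjusted. With d in single-score SDs the noncentrality is d√8/√(2(1 − rho)) against d√8/√((1 − rho²)·29/28). At d = 0.75 and rho = 0.5 this is 2.12 against 2.41. With d in change-score SDs, multiply d by √(2(1 − rho)) first. Here d = 0.75 is half the planned effect.

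| d and its SD scale | rho 0.2 | rho 0.5 | rho 0.9 |
|---|---|---|---|
| 0.75, single score | 37 → 54% | 54 → 64% | 99.6% both |
| 0.75, change score | 54 → 74% | 54 → 64% | 54% both |
| 1.5, single score | 90.1 → 98.4% | 98.4 → 99.6% | near 100% both |
| 1.5, change score | 98.4 → 99.9% | 98.4 → 99.6% | 98.4 → 98.5% |

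**Gate and B21 together.** I assume the same rho between all visits, a mid-treatment effect of half d, d = 0.75 in single-score SDs and an exact F gate. The simulated chance that the gate passes and B21 is significantly negative rises from 30% to 44%, from 42% to 52%, and from 99.3% to 99.4% at the three rho values.

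**Gate size.** With a correct covariance and 32 women, a chi-square gate rejects 9.0–9.3% under no effect, both with B01 (5 df) and without it (4 df). An exact F gate rejects 4.9–5.1% in both cases. B01 is therefore not the source of that excess; the chi-square reference is.

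**The printed covariance, a separate fault.** With no random term on P0 and independent E, the model forces zero covariance between baseline and every follow-up visit. Two results follow.
- Read literally (ML, chi-square gate, 32 women), simulated gate size is 7.7%, 8.5–8.9% and 12.8–12.9% at rho 0.2, 0.5 and 0.9. At 200 per arm it is still 5.5%, 6.6% and 11.5%, where a correct covariance gives 5.0–5.2%. The size of the B21 test falls to 3.3–5.0%, 1.1–1.7% and 0%. Its power at d = 0.75 is 31–38% at rho 0.5 and 25–37% at rho 0.9.
- If only B01 is deleted, the printed covariance leaves a follow-up-only comparison. With k = 1 its variance is 1/(2(1 − rho)) times that of raw change: 1/0.8 = 1.25 at rho 0.6 and 1/0.6 = 1.67 at rho 0.7.

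**The case against.** A response-profile model with a free baseline difference is a recognised, unbiased analysis, and the plan says that it wants change from baseline. The model does subtract baseline; what it lacks is a baseline covariate or a common baseline mean. That is correct, and it is why this point is optional.

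The savings rest on values the documents do not give. That also stands: with 32 women the cases shown run from a 51.8% saving to 3.6% more variance. At the planned d = 1.5, power is already 98.4% or more, unless rho is below 0.5 and d is in single-score SDs. The lone effect of dropping B01 from the gate is modest: with an exact F gate at d = 0.75, gate power goes from 60% to 66% (rho 0.2), from 62% to 67% (0.5) and from 99.7% to 99.8% (0.9).

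The printed covariance is arguably the larger problem. At d = 0.75 and rho 0.5, repairing it alone takes B21 power from 31–38% to 54%; the common baseline mean adds the step to 64%. At rho 0.9 the repair does all the work. This is a reason to make the edits together, not to omit one.

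Finally, a common baseline mean relies on baseline answers not being influenced by the allocation. Suppose knowing the arm shifts baseline by 0.3 SD, with rho 0.5. If the shift persists to follow-up, raw change is unbiased and adjustment is off by 0.30 − 0.5 × 0.30 = 0.15 SD. If it affects baseline only, raw change is off by 0.30 SD and adjustment by 0.15 SD. The comparison cuts both ways and is settled by the order of procedures. Section 8.3 says "Participants will be asked to complete questionnaires at baseline, mid-treatment (after 6 sessions") but does not place the baseline questionnaires before randomisation.

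**Conclusion.** The concern holds as an optional improvement in efficiency, with medium confidence in its size. The plan estimates a baseline difference that cannot reflect therapy, includes it in the gate and nowhere adjusts for the baseline score. With equal SDs and 32 women, adjustment would save about 38%, 22% or 2% of the variance of B21, B31 and B41 at rho 0.2, 0.5 or 0.9. The saving is larger if follow-up scores vary less than baseline scores, and otherwise generally smaller across the range shown. The gain matters mainly if the effect falls well short of d = 1.5. The figures assume complete data and a covariance that links baseline to follow-up, so they do not describe the model exactly as printed.

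**What to change.** Edit section 8.5 as one package, before any analysis by arm:

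1. Set P0 = B00, one common baseline mean, in both the full and the reduced model.
2. Replace E and R1–R4 with an unstructured 5 × 5 within-person covariance.
3. Gate on B11, B21, B31 and B41 only.
4. Name a small-sample F reference for the gate, including the method to be used when visits are missing. Steps 1 to 3 do not cure the chi-square excess.
5. State that baseline questionnaires are completed before the arm is known.

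Do not delete B01 on its own.

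The common-mean form keeps women who have only baseline data, as the missing-data paragraph requires. A follow-up-only model with the baseline score as covariate is an alternative only if its slope may differ by visit. It drops women with no follow-up and gives no protection if step 5 fails.

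The cost is a few linked edits and one sentence on procedure, with no new data. The downsides are 15 covariance parameters instead of 11 in about 32 women, and up to 3.6% more variance (complete data) if rho times the SD ratio happens to equal 1.

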## **15.0 Risks to Participants:**

Participating in this study involves minimal risks. It is possible that participants may feel some shame, emotional discomfort, distress, boredom/fatigue when completing the assessments of urinary symptoms, depression, and anxiety, or when participating in therapy. If we find that participants in the study are at risk for harming themselves or others, we will follow the protocol to connect the participant with crisis services, and document the situation accordingly. We will inform participants that their participation in this study may result in a loss of privacy. This includes data from questionnaires entered into a computerized database, questionnaires completed online, as well as written therapy notes. Several steps will be taken to protect confidentiality and minimize the above risks.

If a participant withdraws from any part of the study (e.g., does not complete one of the surveys), they are welcome to participate in other aspects of the study. If a participant chooses to withdraw from the study, data that has been collected during their participation will be analyzed unless the participant specifies otherwise.

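### The HLM result labelled intent-to-treat can overstate the effect of assignment to UP-CBT if women who stop therapy lose benefit and their later outcomes are not collected

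*Combined protocol and SAP*

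**What the plan says.** Missing data are covered by two sentences in section 8.5 (Analysis Plan). The first sets the population: "All participants with baseline data will be included in the modeling using an intent-to-treat approach". The second sets the method: "The HLM approach described above can accommodate cases with missing follow-up data". The section does not name the missing-data assumption, does not say which effect is estimated for women who stop therapy, and plans no sensitivity analysis. The key parameters are B21, B31 and B41 (post-treatment, 3 months, 6 months) for both primary outcomes, PROMIS anxiety and UDI-6.

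Other sections bear on how much will be missing:

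- Section 4.0 (Sample Size): "Study withdrawal is estimated at roughly 20%, leaving an estimated final sample of 32 participants for data analysis".
- Section 8.3 (Measures) ties the mid- and post-treatment questionnaires to completing 6 and 12 sessions. The 3- and 6-month follow-ups are online, through an emailed link.
- Section 12.0 (Financial Compensation) pays $15 for each follow-up, separately from the therapy sessions. For a woman who withdraws, it mentions only payment in proportion to sessions completed.
- Section 15.0 (Risks to Participants) allows a woman who drops out of one part to continue with the rest. For those who leave the study, "data that has been collected during their participation will be analyzed unless the participant specifies otherwise".

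**The concern.** Putting a woman's baseline score into the model does not by itself make the estimate an effect of assignment. A likelihood HLM is valid under missing at random. It fills the gap after her last score with the course expected of women in the same arm who are still observed and share her observed history. If nobody is measured after stopping therapy, that is in effect the course on therapy.

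This equals the effect of assignment only if women who stop UP-CBT do as well afterwards as those who continue. Section 8.4 (Therapy) gives reason to doubt it: skills are taught across 12 sessions, relapse prevention comes late, and only the UP-CBT arm has homework. Section 1.3 (Hypotheses) expects no average improvement under supportive therapy, so any lost benefit would fall mainly on the UP-CBT arm.

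What is at stake is the size of the effect reported for Aim 1, under a label that readers take to cover everyone randomised. As the plan stands, no analysis would show how far the result depends on this assumption.

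**Working it through.** **1. The plan's own figures.** Section 4.0 states: "we would require 16 women per group, in the data analyzed, to detect a treatment effect", with power above 98% at d = 1.5 and two-sided alpha 0.05. The noncentrality is 1.5 × √(16/2) = 4.24 on 30 degrees of freedom, which gives power 0.984 (normal approximation 0.989). Enrolment: 40 × 0.80 = 32. Both figures reproduce.

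**2. Inputs for the check.**

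- From section 4.0: d = 1.5, withdrawal w = 0.20.
- Assumed, because the documents give no figure: k, the share of benefit kept by women who stop UP-CBT; and r, the share of withdrawn women whose later outcomes are collected. Each is varied from 0 to 1.
- Also assumed: d = 1.5 is the effect on therapy, withdrawal is equal in both arms, and control women have no benefit to lose.

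**3. Formulas.**

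- Effect of assignment = d × [(1 − w) + w·k]
- Model estimate = d × [(1 − w) + w·r·k] / [(1 − w) + w·r]

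**4. Results at w = 0.20 (SD units).**

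| Benefit kept (k) | Outcomes collected (r) | Effect of assignment | Model estimate | Overstatement |
|---|---|---|---|---|
| 0 | 0 | 1.5 × 0.8 = 1.20 | 1.5 × 0.8/0.8 = 1.50 | 25% |
| 0 | 0.5 | 1.20 | 1.5 × 0.8/0.9 = 1.33 | 11% |
| 0 | 1 | 1.20 | 1.5 × 0.8/1 = 1.20 | 0 |
| 0.5 | 0 | 1.5 × 0.9 = 1.35 | 1.50 | 11% |
| 0.5 | 0.5 | 1.35 | 1.5 × 0.85/0.9 = 1.42 | 5% |
| 1 | any | 1.50 | 1.50 | 0 |

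In the extreme case (k = 0, r = 0), the overstatement is 11% with 10% withdrawal (1.50 against 1.35) and 43% with 30% (1.50 against 1.05).

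**5. Check by simulation.** The set-up was 40,000 records, five time points, an assumed correlation of 0.6 and maximum likelihood with arm-by-time means. It was run with an unstructured covariance and with the printed structure, which has no random intercept. With full loss of benefit and no later outcomes, B21, B31 and B41 came out at about −1.50 against a true effect of about −1.20. This held for withdrawal before session 6, after session 6, and when withdrawal was more likely after a high mid-treatment score. Collecting half of the withdrawn women's outcomes gave about −1.33. Collecting all of them gave the true value.

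**6. When the mid-treatment score already shows no benefit.** The observed history then corrects part of the error. Assume correlations of 0.5 (baseline with each later score) and 0.7 (mid with post), and a usual mid-treatment benefit of 0.75 SD. The slope of post on mid given baseline is (0.7 − 0.25)/(1 − 0.25) = 0.6. The model credits these women with 1.5 − 0.6 × 0.75 = 1.05 and returns 0.8 × 1.5 + 0.2 × 1.05 = 1.41. Against 1.20 the excess is 0.21, or 17.5%.

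**7. Effect on the test.** With d = 0 both formulas give zero. At a true 1.20 SD, two-sample t-test power is 91% with 16 per group and 96% with 20.

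**The case against.** The strongest reply is that stopping therapy is not the same as having no outcomes. Section 15.0 lets a woman who leaves one part continue with the others, and the two follow-ups need only an emailed link and carry their own payment. Scores obtained this way enter the HLM and shrink the bias, to zero if complete. This stands. A reader might infer that the HLM always estimates the effect as if everyone had stayed in therapy; the documents do not support that, least of all for B31 and B41. They support a conditional statement, because section 15.0 gives permission but sets out no active follow-up. B21 is the most exposed, since its questionnaire depends on reaching session 12.

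Three further replies also stand:

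- **No false positive.** A reader might infer that the plan could declare an ineffective therapy effective. With no effect there is no benefit to lose, so this mechanism cannot do that, and power at 1.20 SD stays high. The issue is effect size and labelling.
- **The 32 and the 40.** Sections 4.0, 8.5 and 15.0 might be read as three conflicting analysis populations. Section 4.0 gives a planning count for power, section 8.5 defines who enters the model, and section 15.0 gives a participant an option over her own data. Only the wording of 4.0 needs aligning.
- **Loss of benefit is unknown.** Full loss is as untestable as missing at random. Section 8.4 describes general coping skills, so part of the benefit may last. Section 8.4 also says supportive therapy may help some women; if those who stop it lose a benefit too, the bias is smaller.

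**Conclusion.** The point holds in conditional form. If women who stop UP-CBT lose benefit and their later outcomes are missing, B21 overstates the effect of assignment, and so do B31 and B41 to the extent that the online follow-ups are missed. The range in the table, zero to 25% of the true effect, rests on d = 1.5 as the on-therapy effect, 20% withdrawal equal in both arms, and no control benefit lost. The 25% is an extreme and should not be quoted as the expected bias, because nothing in the documents fixes either the benefit lost or the share of outcomes collected.

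The HLM remains a reasonable primary model. The gap is that its assumption is unstated and untested, and that outcome collection after therapy stops is allowed but not planned. This should be corrected, but it does not invalidate the trial.

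**What to change.** In section 8.5:

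1. Keep the HLM as the primary model and state that it assumes missing at random.
2. State that questionnaires will be sought from all randomised women at matching calendar times (about weeks 6 and 12, and at the 3- and 6-month follow-ups), whether or not they are still in therapy, and that these scores enter the model. Align section 8.3 with this. It is the most direct remedy, because it removes the cause.
3. Prespecify one sensitivity analysis for B21, B31 and B41 on both primary outcomes: either reference-based imputation of missing UP-CBT scores from the supportive-therapy profile, or a delta shift applied to them. Report it beside the primary result. It should not be a gate on the effectiveness claim: with about four women missing per arm (20% of 20) and an untestable assumption on either side, that would be a debatable trade-off.

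In section 4.0, reword the count to: up to 40 analysed, about 32 expected with complete data.

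The cost is a little more analysis and follow-up contact, and a sensitivity estimate that may be less favourable than the primary one.
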